Wet-to-dry vs Petrolatum & Non-stick Dressings After Hidradenitis Suppurativa Surgery

 NCT number
 NCT05194969

 Document Date
 8/1/2024

PROTOCOL: INTERVENTIONAL STUDY

Complete Title: Comparison of Wet-to-dry vs Petrolatum and Non-stick Dressing for Second Intention Healing Following Hidradenitis Suppurativa Surgery

Short Title: Wet-to-dry vs Petrolatum & Non-stick Dressings After Hidradenitis Suppurativa Surgery

Drug or Device Name(s):

FDA IND/IDE (if applicable):

Sponsor: University of North Carolina, Chapel Hill

Protocol Date: 8/1/2024

Study Principal Investigator [name] UNC School of Medicine Department of Dermatology [name] [contact] email: [contact]

ABBRE	VIATIONS AND DEFINITIONS OF TERMS	
PROTO	DCOL SYNOPSIS	4
васко	GROUND AND RATIONALE	7
1	STUDY OBJECTIVES	9
2	INVESTIGATIONAL PLAN	
3	STUDY PROCEDURES	
4	STUDY EVALUATIONS AND MEASUREMENTS	
5	STATISTICAL CONSIDERATIONS	
6	STUDY INTERVENTION (DEVICE, DRUG, OR OTHER INTERVENTION)	
7	STUDY INTERVENTION ADMINISTRATION (IF APPLICABLE)	
8	SAFETY MANAGEMENT	
9	DATA COLLECTION AND MANAGEMENT	
10	RECRUITMENT STRATEGY	
11	CONSENT PROCESS	
12	PLANS FOR PUBLICATION	
13	REFERENCES	
APPEN	IDIX	

Abbreviations and Definitions of Terms

Abbreviation	Definition
HS	Hidradenitis Suppurativa
MID	Minimal important difference
NRS	Numeric Pain Rating Scale
PUSH	Pressure Ulcer Scale for Healing
PWAT	Photographic Wound Assessment Tool

PROTOCOL SYNOPSIS

Study Title	
Funder	UNC Department of Dermatology
Clinical Phase	NA
Study Rationale	Hidradenitis suppurativa (HS) is a chronic, severe, inflammatory skin condition characterized by recurring abscesses, nodules, and tunneling sinuses in intertriginous locations such as the groin, buttocks, and axillae. While many patients are managed with medications and lifestyle modifications alone, a subset of HS patients benefit from surgical intervention. Proper wound care following HS surgery is paramount, as facilitating proper healing and minimizing infection can prevent post-operative complications, morbidity and the need for future procedures. This study hopes to answer the question of whether wet-to-dry dressings should be standard of care or whether an alternate form of wound dressings, such as petrolatum with non-stick bandaging, is at least equitable if not superior in effect with fewer drawbacks.
Study Objective(s)	Primary Objectives: - Characterize and compare the 2 regimens via patient-
	 Characterize and compare the two bandaging regimens in terms of wound healing after surgical deroofing and excisional procedures using the validated PUSH tool

 Characterize and compare the 2 bandaging regimens in terms of pain with dressing changes, as measured by the NRS, after surgical deroofing procedures

Test Article(s)	NA
(If Applicable)	
Study Design	Interventional Study Model: Parallel Assignment
	 This study is a randomized, blinded trial of two postoperative bandaging techniques after HS surgery: wetto-dry dressings vs. petrolatum with non-stick bandaging. Patients will be followed for a minimum of 6 weeks postoperatively with surveys to be completed at home, including a wound photograph, at weeks 1, 2, 4, and 6 weeks postoperatively. If wounds have not healed by week 6, then final healing may be tracked up to 12 weeks to monitor for complications.
	Number of Arms: 2
	Masking: Triple (Care Provider, Investigator, Outcomes Assessor)
	 Following the surgical procedure, the principal investigator (PI) exits the exam room. The PI is not present for bandaging administration and training and thus is blinded to the wound dressing technique. The patient is not blinded as bandaging will be administered at home.
	Allocation: Randomized
	Enrollment: 74
Subject Population	Accepts Healthy Volunteers: No
key criteria for Inclusion	Inclusion Criteria:
and Exclusion:	 Male & females ≥ 16 years of age
	 Patient must have undergone a standard-of-care surgical procedure for HS with planned secondary intention healing of the wound.
	 Must be able to provide adequate informed consent for themselves
	 Must be capable of performing either of the recommended wound care regimens on their own or have someone available to consistently assist with wound care.
	Exclusion Criteria:
	 Patients with surgically closed wounds (sutures, staples)
	 Patients with preference for specific types of bandaging protocols
	 Patients that have not been able to tolerate either wet-to- dry or petrolatum and non-stick bandages in the past

Number Of Subjects	74
Study Duration	Each subject's participation will last at least 6 weeks. Official Dates: April 25 th , 2022 – October 30 th , 2023 (18 months)
Study Phases Screening Study Treatment Follow-Up Efficacy Evaluations	Study Phases: Phase 1 (Day 0): Screening and Enrollment Phase 2 (Weeks 1–Wound closure): survey completion and wound monitoring Phase 3: Data Analysis Primary efficacy evaluation will be completed using the validated PUSH tool, NRS tool, and Wound QOL survey.
Safety Evaluations	Monitoring for signs of wound infection will be included on regularly scheduled patient surveys. If pain scores become worse following bandaging within one of the wound dressing groups during periodic data reviews, then we may need to stop the study early if this becomes significant. Subjects will have the ability to contact us with any concerns and should other unanticipated adverse events be reported we will track them and address any serious adverse events or trends.
Statistical And Analytic Plan	The general goal is to demonstrate non-inferiority between the two bandaging types. The PUSH tool is the primary endpoint utilized to power for non-inferiority between the two wound bandaging techniques. There is no a-priori rationale for any exact non- inferiority margin. Instead, it is estimated that the expected half- width of a 97.5% confidence interval (i.e., the lower extension of a one-sided, Bonferroni-adjusted 98.75% CI) will be 0.61 SDs. Put differently, there would be 80% power to establish that the non- stick dressing is not 0.84 SDs worse than the wet to dry dressing. Utilizing the sample size of 74 patients calculated using the non- inferiority analysis for the PUSH tool actually provides the study sample size necessary to reliably identify a meaningful difference between the other two primary endpoints, the NRS tool and Wound QOL survey. Primary outcome measures will be reported as means and full ranges.
DATA AND SAFETY Monitoring Plan	We will be compiling and monitoring data on responses on an ongoing basis and reviewing every 2-3 weeks. If one group is demonstrating significantly worse outcomes before the planned end of the enrollment period, we will end the study early and report the results available at that time. All patient data collected in this study will be stored within the secure research software RedCap. Data access will be restricted to the research fellow as the primary data input source. Downloaded

data will be secured on the UNC hospital cloud and only deidentified data will be sent via email. The principal investigator will not have access to any patient data until the de-identified data is provided for analysis at the conclusion of the study. Data will be coded according to established coding protocol.

BACKGROUND AND RATIONALE

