There are approximately 6-8 new patients per week, and we conservatively estimate at least 2 will consent to the study. Thus, we should be able to reach our desired sample size in 36 weeks. With 6 weeks of required follow-up, the last patients should be finished by 42 weeks, well within 1 year. If our recruitment and/or retention is better, we will continue to gather data, again yielding better power. Our other primary endpoint is efficacy. We believe the non-stick dressing will not lead to reduced wound healing compared to the traditional wet to dry dressing. We don't have an a-priori rationale for any exact non-inferiority margin. Instead, we estimate that the expected half-width of a 97.5% confidence interval (i.e., the lower extension of a one-sided, Bonferroni-adjusted 98.75% CI) will be 0.61 SDs. Put differently, we would have 80% power to establish that the non-stick dressing is not 0.84 SDs worse than the wet to dry dressing.

Aim 1. Characterize and compare the 2 bandaging regimens in terms of pain with dressing changes after a surgical deroofing procedure

Hypothesis for Aim 1: Rating of pain will be less in the petrolatum and non-stick bandaging group compared to the wet-to-dry group

We are using the numerical rating scale (NRS) for pain that ranges from 0-10. From prior studies on the NRS, we know that the minimal clinically significant difference in pain on the scale is approximately 1.3 points [6]. We believe the non-stick dressing will reduce pain ratings by 1.3 points at the two-week checkup and estimate the historical standard deviation between patients pain ratings at that visit is 1.4 units, implying a .93 SD reduction. Our ability to detect this difference and achieve 80% power is far exceeded by the 74 patients needed to detect non-inferiority via the PUSH tool (see Aim 3). We will report means and full ranges for NRS values in each group across relevant time points.

Aim 2. Characterize and compare the 2 regimens via patient-centered outcomes outlined in the validated Wound QOL Survey and additional questions

Hypotheses for Aim 2: Patient QOL ratings will be more favorable in the petrolatum and non-stick bandaging group compared to the wet-to-dry group

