The minimal important difference (MID) in Wound-QoL-17 overall score was determined in a German sample of 227 patients with chronic wounds and was found to be approximately 0.5 [4]. This means that a decrease of the Wound-QoL-17 total score of 0.50 or more in a group of patients can be assumed to indicate patient-relevant change. The global score ranges from 0 (= no impairment) to 4 (= maximum impairment). Preliminary statistical analysis indicated that we would need only 3 patients in each study arm to detect this difference. As a result, the study sample size necessary to meet this number to achieve 80% power is far exceeded by the 74 patients needed to detect non-inferiority via the PUSH tool (see Aim 3). We will report means and full ranges for Wound-QOL values in each group across relevant time points.

Aim 3. Characterize and compare the two bandaging regimens in terms of wound healing after surgical deroofing and excisional procedures using the validated PUSH and PWAT tools

Hypotheses for Aim 3: Wound healing in the petrolatum and non-stick bandaging group will be noninferior compared to the wet-to-dry group

The pressure ulcer scale for healing (PUSH) tool is a well-validated and accurate measure of healing for chronic wounds that heal by secondary intention. However, it has not been used frequently by the principal investigator as a measure of wound healing. Given our unfamiliarity in the clinical variance of PUSH scores between patients, we plan to power for non-inferiority between the two wound bandaging techniques in terms of wound healing as opposed to superiority of one bandaging type over the other. We don't have an a-priori rationale for any exact non-inferiority margin. Instead, we estimate that the expected half-width of a 97.5% confidence interval (i.e., the lower extension of a one-sided, Bonferroniadjusted 98.75% CI) will be 0.61 SDs. Put differently, we would have 80% power to establish that the non-stick dressing is not 0.84 SDs worse than the wet to dry dressing.

The photographic wound assessment tool (PWAT) is not a primary endpoint for which the study is powered, but it will still be completed and analyzed as a secondary outcome of interest and reported as means and full ranges.

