6 STUDY INTERVENTION ADMINISTRATION

- Randomization procedures

A stratified block randomization will take place after the principal investigator has left the surgical room following surgery. Randomization will be performed by the research fellow. Each participant is assigned to a particular stratum based on wound size and location, two important covariates to control for in statistical analysis given these variables can impact the Wound QOL survey and other results significantly. After strata assignment, randomization is completed via a RedCap algorithm. A detailed outline of the randomization process and groups can be found in **Figure 1**.

- Blinding procedures

Following the surgical procedure, the principal investigator will exit the exam room. The principal investigator will thus be blinded to the wound dressing technique as he will not be present for bandaging administration, but the patient will not be blinded as they themselves will be administering the bandaging at home.

- Unblinding procedures

If at any point unblinding occurs, the involved patient will be notified that their further participation in the study is voluntary but their patient data can no longer be used for analysis. There is no penalty or direct harm anticipated to the patient because of unblinding. They can continue to bandage their wound as assigned during randomization or alternatively if desired.

- Premature Study Closure

If any of the groups are showing significantly worse outcomes with regard to changes in pain or days to surgical wound resolution before the end of the recruitment period, the study will be ended prematurely.

- Subject Withdrawal

If a subject fails to complete a their one-week postoperative survey or are unable to complete the assigned wound care for a full week, they will be withdrawn from the study. All subjects will have the option to withdraw from the study at any time that they wish.

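### The only stated output for the primary endpoints is arm means and full ranges; the confidence interval and covariates used in planning are not carried into a final analysis

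*Combined protocol and SAP*

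**What the plan says.** The Statistical and Analytic Plan row of the Protocol Synopsis ends with the sentence "Primary outcome measures will be reported as means and full ranges". In Statistical Considerations, Aim 1 adds "We will report means and full ranges for NRS values in each group across relevant time points" and Aim 2 adds "We will report means and full ranges for Wound-QOL values in each group across relevant time points". Aim 3 has no such sentence for PUSH. Its only mention of means and ranges concerns PWAT, a secondary outcome.

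The hypotheses are comparative:

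- Aim 1: "Rating of pain will be less in the petrolatum and non-stick bandaging group compared to the wet-to-dry group".
- Aim 2: "Patient QOL ratings will be more favorable in the petrolatum and non-stick bandaging group compared to the wet-to-dry group".
- Aim 3: "Wound healing in the petrolatum and non-stick bandaging group will be noninferior compared to the wet-to-dry group".

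Inferential elements appear only in planning or design text. The synopsis and Statistical Considerations give an expected half-width of 0.61 SD for a Bonferroni-adjusted 97.5% interval, and 80% power to rule out a 0.84 SD deficit. They also say "We don't have an a-priori rationale for any exact non-inferiority margin". The opening paragraph of Statistical Considerations adds patients for two planned covariates, location and initial wound size. Section 6, under Randomization procedures, calls wound size and location "two important covariates to control for in statistical analysis".

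**The concern.** A mean with a minimum and maximum describes one arm. Two superiority hypotheses and one non-inferiority hypothesis each need an estimated difference between arms with its precision. The full range rests on the two most extreme patients and tends to widen as more patients respond, so it is a poor stand-in for an SD. Raw arm means also leave out the two covariates that the plan itself says to control for.

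At stake is whether the stated results could answer any of the three aims. A second issue is how much is left open. With three primary endpoints and four survey visits (weeks 1, 2, 4 and 6), the visit, model and confidence level could all be chosen after the data are seen.

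**Working it through.** **Inputs from the Protocol.** 28 patients per arm; pain difference 1.3 points with SD 1.4; 97.5% interval with half-width 0.61 SD; 0.84 SD excluded with 80% power (all in Statistical Considerations). Three primary endpoints (Primary Objectives).

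**1. Reproduce the plan's precision figures.** With 1:1 allocation and SD = 1, the standard error of a difference is sqrt(2/n) = sqrt(2/28) = 0.267 SD. The half-width is t(0.9875; 2n − 2) × sqrt(2/n):

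| n per arm | half-width (SD) |
|---|---|
| 28 | 2.306 × 0.267 = 0.616 |
| 29 | 2.303 × 0.263 = 0.605 |
| 30 | 2.301 × 0.258 = 0.594 |

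The stated 0.61 is reproduced. By noncentral t at one-sided alpha 0.0125 and 28 per arm, the deficit excluded with 80% power is 0.844 SD, against 0.84 stated. The planning arithmetic is sound on this point.

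**2. What that interval would deliver if reported.** For NRS with SD 1.4, the half-width at 28 per arm is 1.4 × 0.616 = 0.86 points. An observed difference of 1.3 points would have a 97.5% interval of 1.3 ± 0.86, or 0.44 to 2.16. The sample size therefore supports an inferential analysis.

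**3. What means and ranges deliver.** Assumed data, 28 per arm: arm A has mean 4 and range 0 to 8; arm B has mean 5 and range 1 to 9. Two data sets share these summaries exactly.

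- One patient at each extreme and 26 at the mean: SD = sqrt(2 × 4²/27) = 1.09, SE of the difference = 1.09 × 0.267 = 0.29, p = 0.001, 97.5% interval 0.33 to 1.67.
- Half the patients at each extreme: SD = sqrt(28 × 4²/27) = 4.07, SE = 4.07 × 0.267 = 1.09, p = 0.36, 97.5% interval −1.51 to 3.51.

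These are deliberately the two limiting cases. They show that the planned summaries do not fix the standard error: here it can differ by a factor of 4.07/1.09 = 3.7.

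**4. Confidence level.** A 97.5% interval corresponds to 0.05/2, that is, Bonferroni across two comparisons. Across all three primary endpoints the level is 1 − 0.05/3 = 98.3%. The half-width at 28 per arm is then t(0.9917; 54) × 0.267 = 2.471 × 0.267 = 0.66 SD.

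**5. PUSH.** Higher PUSH scores are worse (Primary Objectives). For non-stick minus wet-to-dry, non-inferiority therefore turns on the upper confidence bound. The plan gives no margin to compare it with. The 0.84 SD is what the sample could exclude with 80% power, not a justified margin.

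**The case against.** The strongest reply is that a sentence about reporting is not the whole analysis. It does not say that nothing else will be produced. The synopsis refers to a non-inferiority analysis for PUSH, Statistical Considerations refers to a main analysis and planned covariates, and Section 6 calls for covariate control. All this stands. A reader might infer that the sponsor chose to decide the hypotheses from ranges, or planned no inference; the documents do not support that. Nor do unadjusted descriptive means contradict an adjusted analysis. What remains is an omission: a sample-size precision statement does not specify an estimate, visit, model or decision rule, and no other text does.

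A reader might also infer that a range carries no information about precision. That goes too far. In simulated normal data at 28 per arm, the expected range is 4.03 SD. Dividing the two arms' average range by 4.03 recovers the standard error of 0.267 SD on average, with a 95% interval of 0.21 to 0.34. This back-calculation depends on normality, though, and NRS (0–10), Wound-QoL (0–4) and PUSH (0–17) are all bounded and discrete.

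Finally, it is fair to say that an interval alone does not settle non-inferiority. Without a margin, even a well-estimated PUSH difference cannot support that conclusion.

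**Conclusion.** The point holds as a gap in specification. Means and full ranges are the only stated output for the primary endpoints, and the interval and covariates behind the design are not carried into a stated final analysis. Reported as written, the results could not decide Aims 1, 2 or 3.

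The example from p = 0.001 to p = 0.36 rests on assumed data at the limits of what the summaries allow. It shows that the answer is not determined; it does not predict what this trial will find. The reproduced half-width assumes a two-sample t interval with equal arms and a common SD. No error in the 0.61 or 0.84 SD figures is claimed. The gap is widest for PUSH, which has neither a reporting sentence under Aim 3 nor a margin.

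**What to change.** Amend the synopsis sentence and those under Aims 1 and 2, and add one for PUSH under Aim 3, along these lines:

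- Each primary endpoint is reported as arm means with SDs, plus the difference (non-stick minus wet-to-dry) adjusted for location stratum and initial wound size.
- The difference carries at least the plan's own 97.5% interval, or 98.3% if Bonferroni is applied across all three primary endpoints.
- NRS is compared at week 2, the visit on which pain is powered. One primary visit each is named for Wound-QoL and PUSH. A covariate-adjusted comparison at that visit is enough; a repeated-measures model is optional.
- For PUSH, the upper bound of the difference is read. Either a margin is stated with its rationale, or the difference and interval are reported without a claim of non-inferiority.
- Ranges stay as descriptive extras.

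No new data are needed, only wording and routine analysis. Moving from 97.5% to 98.3% widens the half-width from about 0.62 to 0.66 SD at 28 per arm. The document is dated 8/1/2024, after the official end date of October 30th, 2023, and gives actual enrollment as 74. The amendment should therefore say when each element was fixed relative to anyone seeing the data, and anything fixed afterwards must be labelled post hoc.

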1.1 Introduction

Hidradenitis suppurativa (HS) is a chronic, severe, inflammatory skin disease associated with pain, drainage, odor, and disability characterized by recurring abscesses, nodules, and tunneling sinuses in intertriginous locations such as the groin, buttocks, and axillae. HS has more negative impact on patients' quality of life than all other common dermatologic diseases and is common, affecting ~1% of the general population, with higher risk for females (3:1) and Black patients. The onset is often in adolescence. As HS has been under-studied historically, there is an unmet medical need to develop more effective treatment for this disease. While many patients are managed with medications and lifestyle modifications alone, a subset of HS patients benefit from surgical intervention. Proper wound care following HS surgery is paramount, as facilitating proper healing and minimizing infection can prevent post-operative complications, morbidity and the need for future procedures. While many physicians continue to use wet-to-dry dressings as the standard of care for HS patients postoperatively, it is likely that the drawbacks of this dressing technique outweigh the benefits. This study hopes to answer the question of whether wet-to-dry dressings should truly be standard of care or whether an alternate form of wound dressings, such as petrolatum with non-stick bandaging, is at least equitable if not superior in effect, and associated with fewer drawbacks such as associated pain and time dedicated to dressing changes. This study will be a randomized, single-blind trial of two postoperative bandaging techniques: wet-to-dry dressings vs. petrolatum with non-stick bandaging. Primary outcomes will be tracked using the photographic wound assessment tool (PWAT), pressure ulcer scale of healing (PUSH) tool, and Wound Quality of Life (QOL) Survey. There is potential for this study to apply to surgical interventions outside of HS, as the study addresses the bandaging technique (wet-to-dry) that is standard of care after many surgical procedures.

